11.1.4.7. Extend of exposure to study drug

Counts and percentages of patients having one respectively two applications will be presented as shown in Table 5 for the NexoBrid and the Gel Vehicle arm. A chi-squared test (or in case of small estimated cell counts Fisher's exact test) will be used to test for any differences in the application data between the two treatment groups. Bar plots of the extend of exposure will be shown.

Furthermore, numbers of patients in the NexoBrid arm being exposed to different grams of NexoBrid powder will be displayed.

11.1.4.8. Medical history and concomitant diseases

The concomitant diseases will be classified using the MedDRA dictionary. They will be tabulated with reference to system organ class and frequency of occurrence (see Table 9). A similar analysis will be conducted but on the level of preferred terms instead of system organ class. Concomitant diseases include all active conditions at start of trial (as documented in the medical history). The analysis of medical history conditions will be done and displayed separately for previous and ongoing diseases.

11.1.4.9. Concomitant medication

In this analysis, only the concomitant medication administered during the acute phase (until the 3 months follow-up for each patient) will be analyzed. The number of concomitant medication and patients involved will be tabulated with reference to ATC coding (see Table 11).

11.1.4.10. Central laboratory values

Laboratory measurements obtained prior and after each eschar removal procedure as well as pre-post differences in laboratory values for each eschar removal procedure will be analyzed descriptively with number of subjects, number of missing values, mean, standard deviation, min, max, median and quartiles as presented in Table 4.

As described in Section 10.3.6, laboratory values will be categorized as “abnormal (low)”, “normal” and “abnormal (high)” based on the reference limits of the labs. This categorization will be analyzed by displaying counts and percentages of each category by treatment group and by procedure (see Table 5) for each laboratory value separately.

11.1.4.11. Blood transfusions

The volume of blood transfusions in milliliters (as calculated in Section 10.3.4.4) will be analyzed descriptively with number of units, number of missing values, mean, standard deviation, min, max, median and quartiles as presented in Table 4. The mean volume of blood transfusions between treatment groups will be compared by a one-way analysis of variance. Histograms will be provided to illustrate the distribution of the volume of blood transfusions in the treatment groups.

The volume of blood transfusions will be presented overall, as well as separately for volumes transfused before start of treatment, during the ER period, within 1 week after the ER period and later than 1 week after the ER period.

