2.2. Study Objective

1. To demonstrate the efficacy of enzymatic eschar removal with NexoBrid by providing complete eschar removal as compared with Gel Vehicle,
2. To demonstrate the efficacy of enzymatic eschar removal with NexoBrid by providing earlier complete eschar removal, reduction in patients' surgical burden and its related blood loss as compared to SOC,
3. To assess the safety of NexoBrid compared to SOC, including demonstration that treatment with NexoBrid does not cause an unacceptable level of harm on wound closure outcome and long-term outcomes of cosmesis and function

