9.3.1. Summary of sample size

Although the maximum sample size from the above calculations is a total of 121 patients (65 in the NexoBrid group, 13 in the Gel vehicle group and 43 in the SOC group (to match NexoBrid numbers)), we propose entering larger numbers to provide an extra margin of assurance in achieving positive results on the efficacy outcomes, and adequate information on safety outcomes to allow better benefit vs. risk assessment.

Therefore, we plan a study with total sample size of 175 patients; 75 (NexoBrid) + 75 (SOC) + 25 (Gel Vehicle).

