Unless otherwise specified, all statistical tests will be conducted against a two-sided alternative hypothesis, employing a significance level of 0.05.

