The pain assessment score will be analyzed descriptively with number of units, number of missing values, mean, standard deviation, min, max, median and quartiles as shown in Table 4 and compared between groups with a one way analysis of variance. A graphical representation of the data will be done using histograms. Furthermore, a plot of the mean pain (and the mean change in pain from baseline) over time will be presented.

The analyses will be done for the pain assessments at screening, pre and post eschar removal procedures, at the first 7 daily assessments as well as for the pre-post differences of the daily vital signs assessments (difference to baseline) described in Section 10.3.4.4 separately.

Furthermore, for the pain assessment at screening, pre and post eschar removal procedures and at the first 7 daily assessments the information whether the pain assessment was normal, abnormal (NCS) or abnormal (CS) is given in the eCRF. These classifications will be analyzed separately for each time point of vital signs assessment by displaying counts and percentages by treatment group (see Table 5). The proportion of normal / abnormal (NCS) and abnormal (CS) assessments will be compared between treatment groups using a chi square test (or Fisher's exact test in case of small estimated cell counts).

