11.1.5.4. Incidence of surgically harvested donor site wounds

This is a counting variable, giving the number of donor site wounds per patient. Rates of patients with different numbers of donor site wounds will be analyzed by displaying counts and percentages by treatment group (see Table 5). Furthermore, bar plots will be displayed (see Figure 2). The number of donor site wounds will be compared between treatment groups using a chi square test (or Fisher's exact test in case of small estimated cell counts).

11.1.5.5. % area of surgically harvested donor site wounds

The % wound area of surgically harvested donor site wounds per patient (computed as in section 10.3.5.11) will be analyzed descriptively with number of units, number of missing values, mean, standard deviation, min, max, median and quartiles as shown in Table 4 and compared between groups with a one way analysis of variance. A graphical representation of the data will be done using histograms.

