11.1.5.9. Autograft related parameters

Total number of autografting procedures

The total number of autografting procedures (per patient) will be analyzed by displaying counts and percentages by treatment group (see Table 5). Furthermore, bar plots will be displayed. The distribution of the total number of autografting procedures will be compared between treatment groups using a chi square test (or Fisher's exact test in case of small estimated cell counts).

This analysis will be repeated on a wound level.

Incidence of repeated autografting

This is a binary (yes/no) variable indicating whether the patient had more than one autograft procedure during the study (based on different dates on the same TW). Rates of patients with

more than one autograft procedure will be analyzed by displaying counts and percentages by treatment group (see Table 5). Furthermore, bar plots will be displayed. The proportion of patients with repeated autograft procedures will be compared between treatment groups using a chi square test (or Fisher's exact test in case of small estimated cell counts).

This analysis will be repeated on a wound level.

Area of repeated autografting

The area of repeated autografting per patient will be analyzed descriptively with number of units, number of missing values, mean, standard deviation, min, max, median and quartiles as shown in Table 4 and compared between groups with a one way analysis of variance. A graphical representation of the data will be done using histograms.

This analysis will be repeated on a wound level.

Early autografted wounds

A subgroup analysis will be performed on the subgroup of target wounds that are early grafted (for a definition see Appendix 13.1.1). The primary endpoint, the secondary endpoints "incidence of surgical excision" and "time to complete eschar removal", as well as the safety endpoint "time to complete wound closure" will be analyzed while only taking wounds that are early grafted into account.

Late autografted wounds

A subgroup analysis will be performed on the subgroup of target wounds that are late grafted (for a definition see Appendix 13.1.1). The primary endpoint, the secondary endpoints "incidence of surgical excision" and "time to complete eschar removal", as well as the safety endpoint "time to complete wound closure" will be analyzed while only taking wounds that are late grafted into account.

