11.1.5.10. Duration of hospitalization

The duration of hospitalization will be analyzed descriptively with Kaplan-Meier plots (see Figure 3) and compared between groups with a log rank test.

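### Most supplementary safety and exploratory outcomes get only a test across treatment groups, with no NexoBrid minus SOC estimate or interval

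*SAP*

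**What the plan says.** The third objective in SAP 2.2 begins "To assess the safety of NexoBrid compared to SOC". The general safety and exploratory sections then set these comparisons:

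- **One-way ANOVA.** Transfusion volume (11.1.4.11): "The mean volume of blood transfusions between treatment groups will be compared by a one-way analysis of variance". Vital signs (11.1.4.5) are "compared between groups with a one way analysis of variance". Pain (11.1.4.6), antibiotic days (11.1.4.14), glucose change (11.1.4.17), percent area excised (11.1.5.1) and donor site area (11.1.5.5) follow the same pattern. So do LEFS, QuickDASH, EQ VAS, BSHS-B and POSAS in 11.2 and 11.3.
- **Chi-square or Fisher test on counts.** Donor sites (11.1.5.4): "The number of donor site wounds will be compared between treatment groups using a chi square test". Grafting (11.1.5.9): "The distribution of the total number of autografting procedures will be compared", also by chi-square. Planned and unplanned readmissions per patient (11.1.4.15) are treated alike.
- **Level and sidedness** (section 11): "all statistical tests will be conducted against a two-sided alternative hypothesis, employing a significance level of 0.05".

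The descriptive results go into Tables 4 and 5 (13.2), which list NexoBrid, SOC, Gel Vehicle and a total, with no column for a difference or interval.

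Three safety endpoints are handled differently. Time to wound closure (11.1.4.1) compares NexoBrid with SOC using a 7-day margin. MVSS at 12 and 24 months (11.2.4.2, 11.3.4.3) uses the adjusted NexoBrid-SOC coefficient and its 95% CI against 1.9.

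**The concern.** The safety question is NexoBrid against SOC. An omnibus test over three arms asks whether any arm differs from any other. Its p-value can be small because of the 25 Gel Vehicle patients alone, and it gives no size or direction for NexoBrid against SOC.

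Gel Vehicle is the negative control (7.1.1.1.2), with an anticipated complete eschar removal of 0 to 10% (9.1.1). A Gel difference in later surgery, excised area or transfusion is therefore plausible.

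A non-significant omnibus p-value is just as hard to use for safety, because without an interval it does not show how large a difference remains possible. For counts there is a second problem: a chi-square test on the categories 0, 1, 2, ... ignores that 3 procedures is more than 1.

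**Working it through.** **Inputs.** Arms 75/75/25 (9.3.1); two-sided 0.05 (section 11). The SAP states no power, effect size, SD or event rate for these outcomes, so every effect below is an assumption.

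**The plan's own NexoBrid-SOC figure.** 9.2 gives 43 + 43 for 90% power by Fisher's exact test at 0.24 versus 0.60. Exact enumeration gives 90.4%, so it reproduces. It does not cover the outcomes discussed here.

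**1. Gel alone differs (normal outcome, three-arm ANOVA).** Non-centrality is λ = Σ nᵢ(μᵢ − μ̄)²/σ². With NexoBrid = SOC and Gel shifted by δ SD, λ = (25 × 150/175) δ² = 21.43 δ². The critical F(2,172) is 3.05.

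| δ (SD) | λ | Significant |
|---|---|---|
| 0.5 | 5.36 | 53% |
| 0.6 | 7.71 | 69% |
| 0.8 | 13.71 | 92% |

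**2. Power for a true NexoBrid-SOC difference (normal outcome).** At 0.46 SD the two-arm t-test has non-centrality 0.46/√(2/75) = 2.82 and power 80%. The omnibus F has:

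- Gel equal to either arm: λ = (75 × 100/175) × 0.46² = 9.1, power 77%
- Gel midway: λ = (75/2) × 0.46² = 7.9, power 71%
- Gel beyond SOC by half the difference: λ = 12.5, power 89%

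Over 0.3 to 0.6 SD, with Gel equal to an arm or midway, the loss is about 1 to 11 points. For a binary outcome at 20% versus 40%, the figures are 76% for two arms and 66 to 74% for three.

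**3. Counts.** Simulation with Poisson means 0.8 / 1.25 / 1.0 (NexoBrid / SOC / Gel) and categories 0, 1, 2, 3, 4+:

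- three-arm chi-square: about 39%
- NexoBrid-SOC chi-square: about 53%
- NexoBrid-SOC rank test: about 74%

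Of the 35 points lost, about 21 (74 − 53) come from ignoring order and 14 (53 − 39) from the third arm. With four other sets of means between 0.5 and 1.5 and uncollapsed categories, the three-arm chi-square has 32 to 44%, the two-arm chi-square 45 to 59% and the rank test 69 to 81%. The chi-square was used throughout; the planned switch to Fisher's test for sparse tables was not simulated.

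**4. Transfusion volume, many zeros.** Assumed transfused shares are 8% / 25% / 20%, with log-normal volumes and the same median in each arm. The result depends on the assumed log-scale SD:

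| Log SD | Three-arm ANOVA | NexoBrid-SOC Welch t | NexoBrid-SOC rank test |
|---|---|---|---|
| 0.4 | 68% | 76% | 82% |
| 0.8 | 48% | 58% | 82% |
| 1.0 | 38% | 47% | 81% |

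Both the third arm and the use of means contribute.

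**5. What is not reported.** With 75 per arm, a NexoBrid-SOC 95% CI for a continuous outcome would extend about 1.976 × √(2/75) = 0.32 SD either side.

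**The case against.** **The three-arm reading is an inference.** The SAP never says three-arm for these tests. The layouts do not settle it, because Table 4 is also cited where only NexoBrid and SOC are compared. Section 11.1.5.8 uses a one-way ANOVA for two groups. This stands. Three arms remains the likelier reading, since the SAP names the arms where it wants two (11.1.3, 11.1.4.1, 11.1.4.7). If two arms were meant, the sections still do not say which.

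**The main questions are already covered.** A reader might infer that NexoBrid is never directly compared with SOC on safety or surgical need. The SAP does not support that. The three named safety endpoints are direct comparisons. Surgical excision is second in the hierarchy, with an adjusted odds ratio and 95% CI (11.1.3.1). Transfusions within the Hb windows enter the blood-loss endpoint, tested against SOC (11.1.3.3). The outcomes at issue are supplementary, and 11.2.8 and 11.3.8 call stage 2 and 3 testing exploratory. That lowers the stakes, but exploratory safety data are read mainly through estimates and intervals.

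**Much power is lost throughout.** A reader might infer this too. It is not so for ANOVA on a normal outcome, where the loss is modest and can turn into a gain.

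**Baseline is ignored.** Also not supported: changes from baseline or pre-post differences are planned for pain, glucose and vital signs (10.3.4.4, 11.1.4.5, 11.1.4.6, 11.1.4.17). Covariance adjustment instead of change scores, or a stratified log-rank test for hospital stay, would be a small gain or a preference.

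**Conclusion.** The point holds for the listed supplementary safety and exploratory outcomes only. As written, their tests neither name NexoBrid versus SOC nor yield an estimate with an interval, so they cannot answer the third objective for those outcomes. Read as three-arm tests, they can be significant because of Gel alone, in 53 to 92% of trials for a Gel shift of 0.5 to 0.8 SD.

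Power is a secondary matter. The loss is about 3 to 9 points for normal outcomes at the 80% level when Gel lies at or between the other two arms. It is about 35 points for counts in the main scenario, mostly through ignoring order. For zero-heavy transfusion volume it depends on how skewed the volumes are. The sizes rest on planned arm sizes and assumed effects; the missing contrast and interval rest on the SAP's text alone. The primary and secondary efficacy conclusions are not touched.

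**What to change.** In the listed sections of 11.1.4, 11.1.5, 11.2 and 11.3:

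1. Name NexoBrid versus SOC as the main comparison and NexoBrid versus Gel Vehicle as secondary.
2. Report each difference with a 95% CI: a mean difference for continuous outcomes and a risk difference for proportions. Table 7 already has columns for estimate, standard error, p-value and confidence bounds; these sections need only refer to it.
3. For readmissions, donor sites and grafting procedures, replace the chi-square on categories with a NexoBrid-SOC Wilcoxon test, plus a rate ratio with CI.
4. For transfusion volume, use a NexoBrid-SOC Wilcoxon test plus the mean difference with CI.
5. Name the arms for hospital stay as well, which 11.1.5.10 says is "compared between groups with a log rank test".

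Stratifying the Wilcoxon test by the full design is not advised: 2 × 3 × 5 = 30 cells would leave fewer than one Gel patient per cell on average. The cost is SAP wording and slightly more output. No data collection changes, and these tests stay outside the hierarchy in 11.1.8.

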11.1.4.12. Maintenance of complete wound closure

This is a binary (yes/no) variable (on a wound level). Maintenance of complete wound closure will be analyzed by displaying counts and percentages of wounds maintaining complete wound closure by treatment group (see Table 5). The proportion of wounds maintaining complete wound closure will be compared between treatment groups using a chi square test (or Fisher’s exact test in case of small estimated cell counts). Bar plots of the proportions of wounds maintaining complete wound closure will be shown.

The analysis will be conducted for the information present at month 1 and month 3 after wound closure.

